4.5. Administration of Study Medication

Study drug will be supplied as a lyophilized powder for solution for injection for subcutaneous use only after reconstitution in a pre-filled, dual-chamber, single-use syringe (DCS). The lyophilized nemolizumab (CD14152) powder (39 mg) and solution for reconstitution (0.595 mL) are stored in separate syringe chambers, with each DCS designed to deliver a 30-mg dose of nemolizumab (CD14152) after reconstitution.

This document is confidential.

4.5.1. Study Drug Dosing – Initial Period

Table 4-1 summarizes study drug dosing for the Initial Period, which includes Day 1/Baseline to Week 16.

Table 4-1: Initial Period Dosing By Treatment Group

Group	Treatment	Loading Dose (Day 1/Baseline)	Dose at Week 4, 8, 12	Route	Schedule
1	Nemolizumab (CD14152)	60 mg (two 30 mg injections)	30 mg	sc	Q4W
2	Placebo	Placebo (2 placebo injections)	Placebo	sc	Q4W

Abbreviation(s): Q4W = every 4 weeks; sc = subcutaneous.

4.5.2. Study Drug Dosing – Maintenance Period

At Week 16, subjects who are clinical responders to nemolizumab (CD14152) treatment will be re-randomized (1:1:1) for participation in the Maintenance Period, and assigned by IRT to nemolizumab (CD14152) 30 mg Q4W, nemolizumab (CD14152) 30 mg Q8W, or placebo Q4W. The Q8W group will receive alternating injections of placebo to maintain the blind.

All placebo-treated subjects who responded to Placebo during the Initial Period will continue to receive placebo in the Maintenance Period.

Table 4-2 summarizes study drug dosing for the Maintenance Period after re-randomization, which spans the Week 16 to Week 48 visits.

Table 4-2: Maintenance Period Dosing By Re-randomized Treatment Group

Group	Treatment	Dose	Week(s)	Route	Schedule
1A	Nemolizumab (CD14152)	30 mg	16, 20, 24, 28, 32, 36, 40, 44	sc	Q4W
1B	Nemolizumab (CD14152)	30 mg	16, 20*, 24, 28*, 32, 36*, 40, 44*	sc	Q8W
1C	Placebo	Placebo	16, 20, 24, 28, 32, 36, 40, 44	sc	Q4W

*with placebo injections at Week 20, 28, 36, and 44 to maintain blind

Abbreviation(s): Q4W = every 4 weeks; Q8W = every 8 weeks; sc = subcutaneous.

1.0

CD14152.SPR118161.SAP.V01

Approved 10-Nov-2022 00:00:00

This document is confidential.

Statistical Analysis Plan for Interventional Studies
 Sponsor: Galderma Research & Development, LLC; Protocol No.: RD.06.SPR.118161

4.6. Study Procedures and Flowchart

The study procedures are described in Table 4-3 below:

Table 4-3: Schedule of Assessments:

Periods	Screening	Initial Treatment							Maintenance							Unscheduled Visit ^{a,b}	Follow-up ^{a,d,e}
		2 ^a	3	4 ^a	5	No visit ^c	6 ^{a/} (ET) ^d	7	8	9	10 ^{a,d}	11	12	13	14 ^{a/} (ET) ^d		
Visit	1	2 ^a	3	4 ^a	5	No visit ^c	6 ^{a/} (ET) ^d	7	8	9	10 ^{a,d}	11	12	13	14 ^{a/} (ET) ^d	(as applicable)	(12 weeks after last injection)
Week (relative to baseline)	(2 to 4 weeks before Day 1) ^f	(Day 1)/ Baseline	4	8	12	15	16	20	24	28	32	36	40	44	48		
Window (± days)		0	±3	±3	±5	±0	±5	±5	±5	±5	±5	±5	±5	±5	±5		±5
Informed consent and assent form	X															(X)	
PGx, subject interview, photography consent form(s) (if applicable)	X															(X)	
Inclusion/exclusion criteria	X	X														(X)	
Demographic data	X															(X)	
Medical history, previous therapy, smoking status	X															(X)	
PATIENT-REPORTED OUTCOME ASSESSMENTS																	
DLQI (≥ 17 years) or eDLQI (12-16 years) ^g		X		X			X				X				X		(X)

Statistical Analysis Plan for Interventional Studies

Sponsor: Galderma Research & Development, LLC; Protocol No.: RD.06.SPR.118161

Periods	Screening	Initial Treatment							Maintenance							Unscheduled Visit ^{a,b}	Follow-up ^{a,d,e}			
		2 ^a	3	4 ^a	5	No visit ^c	6 ^a / (ET) ^d	7	8	9	10 ^{a,d}	11	12	13	14 ^a / (ET) ^d					
Visit	1																			
Week (relative to baseline)	(2 to 4 weeks before Day 1) ^f	(Day 1)/ Baseline	4	8	12	15	16	20	24	28	32	36	40	44	48					
Window (± days)		0	±3	±3	±5	±0	±5	±5	±5	±5	±5	±5	±5	±5	±5					(12 weeks after last injection) ±5
HADS/EQ-		X		X			X				X				X					
5D/POEM/ WPAI:AD ^g		X		X			X													
PIQs ^{g,h}		X		X			X													
AD-associated pain intensity and frequency ^g		X		X			X				X				X					
PGAD ^g		X		X			X				X				X					
PGAT ^g				X			X				X				X					
PP NRS/AP NRS/ SD NRS/sleep diary ^{i,j}	X ⁱ														X ^k					
PCS ^{u,k}		X		X			X ^c													
PGIS-P/PGIS-SD ^{l,j}		X		X			X ^c													
PGIC-P/PGIC-SD ^{l,j}				X			X ^c													
Topical AD medication used (daily) ⁱ	X																			
Subject interview (optional) ^l							X													
CLINICAL PHOTOGRAPHS																				
Clinical photographs (optional) ^m		X					X								X					
EFFICACY ASSESSMENTS																				

Statistical Analysis Plan for Interventional Studies
 Sponsor: Galderma Research & Development, LLC; Protocol No.: RD.06.SPR.118161

Periods	Screening	Initial Treatment							Maintenance							Unscheduled Visit ^{a,b}	Follow-up ^{a,d,e}
		2 ^a	3	4 ^a	5	No visit ^c	6 ^b (ET) ^d	7	8	9	10 ^{a,d}	11	12	13	14 ^a (ET) ^d		
Visit	1	2 ^a	3	4 ^a	5	No visit ^c	6 ^b (ET) ^d	7	8	9	10 ^{a,d}	11	12	13	14 ^a (ET) ^d	(as applicable)	(12 weeks after last injection) ±5
Week (relative to baseline)	(2 to 4 weeks before Day 1) ^f	(Day 1)/ Baseline	4	8	12	15	16	20	24	28	32	36	40	44	48		
Window (± days)		0	+3	+3	+5	+0	+5	+5	+5	+5	+5	+5	+5	+5	+5		
EASI	X	X	X	X	X		X	X	X	X	X	X	X	X	X	(X)	
IGA	X	X	X	X	X		X	X	X	X	X	X	X	X	X	(X)	
BSA	X	X	X	X	X		X	X	X	X	X	X	X	X	X	(X)	
SCORAD	X	X	X	X	X		X	X	X	X	X	X	X	X	X	(X)	
SAFETY ASSESSMENTS																	
ACT ^{g,h}	X ⁿ	X ⁿ	X ⁿ	X ⁿ	X ⁿ		X ⁿ	X ⁿ	X ⁿ	X ⁿ	X ⁿ	X ⁿ	X ⁿ	X ⁿ	X ⁿ	(X) ⁿ	X ⁿ
Respiratory examination ^o	X	X	X	X	X		X	X	X	X	X	X	X	X	X	(X)	X
PEF testing ^p	X	X	X ^p	X	X ^p		X	X ^p	X ^p	X ^p	X	X ^p	X ^p	X ^p	X	(X)	X
Physical examination ^q	X	X	X	X	X		X	X	X	X	X	X	X	X	X	(X)	X
Contraceptive counseling ^r	X															(X)	
Height ^s	X			X ^s			X ^s		X ^s		X ^s		X ^s		X ^s	(X) ^s	X ^s
Weight	X						X				X				X	(X)	X
12-lead ECG ^t	X						X				X				X	(X)	X
Vital signs ^u	X		X	X	X		X	X	X	X	X	X	X	X	X	(X)	X
Adverse event reporting ^v	X	X	X	X	X		X	X	X	X	X	X	X	X	X	(X)	X
Concomitant therapy (including contraception)/ medications ^w	X	X	X	X	X		X	X	X	X	X	X	X	X	X	(X)	X

Statistical Analysis Plan for Interventional Studies

Sponsor: Galderma Research & Development, LLC; Protocol No.: RD.06.SPR.118161

Periods	Screening	Initial Treatment							Maintenance							Unscheduled Visit ^{a,b}	Follow-up ^{a,d,e}
		2 ^a	3	4 ^a	5	No visit ^c	6 ^a / (ET) ^d	7	8	9	10 ^{a,d}	11	12	13	14 ^a / (ET) ^d		
Visit	1																
Week (relative to baseline)	(2 to 4 weeks before Day 1) ^f	(Day 1)/ Baseline	4	8	12	15	16	20	24	28	32	36	40	44	48		
Window (± days)		0	+3	+3	+5	+0	+5	+5	+5	+5	+5	+5	+5	+5	+5		
LABORATORY ASSESSMENTS																	
Urinalysis ^v	X	X					X									X	X
Hematology ^v	X	X	X	X			X									X	X
Blood chemistry ^v	X	X	X	X			X									X	X
TB test ^w	X															X	X
Hepatitis B and C test	X															X	X
HIV test	X															X	X
Pregnancy test ^x	X	X	X	X			X	X	X	X	X	X	X	X	X	X	X
FSH ^y	X															X	X
PK, ADA, PD/Biomarkers, and Optional PGx Assessments																	
PK samples ^{v,z}	X	X	X	X			X	X	X	X	X	X	X	X	X	X	X
ADA samples ^{v,aa}	X	X	X	X			X	X	X	X	X	X	X	X	X	X	X
PD samples (blood) for biomarker assessments ^{aa}	X		X				X									X	X
D-Squares samples ^{aa}	X						X									X	X
PGx samples (optional) ^{bb}	X															X	X
STUDY DRUG ADMINISTRATION																	
Randomization	X															X ^{cc}	X
Study drug injection and training ^{dd,ee}	X ^{ff}	X	X	X			X	X	X	X	X	X	X	X	X	X	X

SAP Version: Final Version 1.0, 09-Nov-2022
 Controlled Document ID: 3903A.01, Effective Date 31-Aug-2020
 Filing requirements: TMF

CONFIDENTIAL

Statistical Analysis Plan for Interventional Studies

Sponsor: Galderma Research & Development, LLC; Protocol No.: RD.06.SPR.118161

Periods	Screening	Initial Treatment						Maintenance						Unscheduled Visit ^{a,b}	Follow-up ^{a,d,e}			
		2 ^a	3	4 ^a	5	No visit ^c	6 ^a (ET) ^d	7	8	9	10 ^{a,d}	11	12			13	14 ^a (ET) ^d	
Visit	1																	
Week (relative to baseline)	(2 to 4 weeks before Day 1) ^f	(Day 1)/ Baseline	4	8	12	15	16	20	24	28	32	36	40	44	48	(as applicable)		(12 weeks after last injection)
		Window (\pm days)	0	± 3	± 3	± 5	± 0	± 5	± 5	± 5	± 5	± 5	± 5	± 5	± 5	± 5	± 5	

CONCOMITANT THERAPY

	X ^g	X ^h	X ⁱ	X ^j	X ^k	X ^l	X ^m	X ⁿ	X ^o	X ^p	X ^q	X ^r	X ^s	X ^t	X ^u	X ^v	X ^w	X ^x	X ^y	X ^z	
Moisturizer use																					
Background topical therapy use																					
TCS \pm TCI accountability ^{i,j}	X	X	X	X	X	X	X	X	X	X	X	X	X	X	X	X	X	X	X	X	X

Abbreviations: ACT = Asthma Control Test; AD = atopic dermatitis; ADA = anti-drug antibody; BSA = body surface area; cDLQI = Children's Dermatology Life Quality Index; DLQI = Dermatology Life Quality Index; EASI = Eczema Area and Severity Index; ECG = electrocardiogram; EQ-5D = EuroQoL 5-Dimension; ET = early termination; FSH = follicle-stimulating hormone; HADS = Hospital Anxiety and Depression Scale; HIV = human immunodeficiency virus; IGA = Investigator's Global Assessment; IRR = injection-related reaction; LTE = long-term extension; PCS = pruritus categorical scale; PD = pharmacodynamics; PGAD = Patient Global Assessment of Disease; PGAT = Patient Global Assessment of Treatment; PGIC-P = Patient Global Impression of Change-Pruritus; PGIC-SD = Patient Global Impression of Change-Sleep Disturbance; PGIS-P = Patient Global Impression of Severity-Pruritus; PGIS-SD = Patient Global Impression of Severity-Sleep Disturbance; PIQs = PROMIS® Itch Questionnaires; PK = pharmacokinetics; POEM = Patient-Oriented Eczema Measure; PP NRS = peak pruritus numeric rating scale; PRO = patient-reported outcome; PROMIS® = Patient-Reported Outcomes Measurement Information System; SCORAD = SCORing Atopic Dermatitis; SD NRS = sleep disturbance numeric rating scale; TB = tuberculosis; TCI = topical calcineurin inhibitor; TCS = topical corticosteroid; UPT = urine pregnancy test; WOCBP = women of childbearing potential; WPALAD = Work Productivity and Activity Impairment: Atopic Dermatitis.

Notes:

- ^a Subjects should fast for at least 8 hours before the visit(s) when blood chemistry testing is planned, except for the screening visit.
- ^b Assessments to be conducted at the unscheduled visit depend on the reason for the visit. PK and ADA analyses are obligatory at unscheduled visits that are conducted for safety reasons when safety labs are collected for the management/monitoring of an AE. When series of unscheduled visits is needed for the monitoring of the same safety event, PK and ADA collection is not required if already done at the first unscheduled visit of the series. Additional collection of samples for PK and ADA analysis should be performed per investigator's judgement. Subjects requiring rescue therapy between scheduled visits should return to the clinic for an unscheduled visit for investigator assessments of efficacy before starting rescue therapy.
- ^c Subjects will complete PCS, PGIS-P, PGIC-P, PGIS-SD, and PGIC-SD assessments at Week 15 (prior to the Week 16 visit) for test-retest validation of itch and sleep PRO measures. For PGIS-P and PGIC-P, subjects will complete a single assessment 8 days prior to the Week 16 visit. For PGIS-SD and PGIC-SD, subjects will complete a single assessment 7 days prior to the Week 16 visit. For PCS, subjects will complete the assessment for 14 consecutive days before the Week 16 visit.
- SAP Version: Final Version 1.0, 09-Nov-2022
- Controlled Document ID: 3903A.01, Effective Date 31-Aug-2020
- Filing requirements: TMF

CONFIDENTIAL

Statistical Analysis Plan for Interventional Studies

Sponsor: Galderma Research & Development, LLC; Protocol No.: RD.06.SPR.118161

^d Subjects discontinued prematurely should complete ET assessments according to: Visit 6/Week 16 if during the initial treatment period **or** Visit 14/Week 48 if during the maintenance period **and** a final/follow-up visit 12 weeks after the last study drug injection (for subjects not participating in the LTE study). Subjects who require rescue therapy (with or without study medication discontinuation) must continue with study visits until: Visit 6/Week 16 if during the initial treatment period **or** until Visit 10/Week 32 if during the maintenance period to be considered for LTE eligibility. (If during the maintenance period, rescue is needed after the Week 32 visit, no wait period is required.)

^e The follow-up visit will be conducted for subjects who decline or are not eligible to enter the LTE study and should be conducted 12 weeks after the last study drug injection. (The follow-up visit is not required for subjects who will rollover to the LTE study.)

^f The run-in period begins at least 2 weeks (i.e., 14 days) before Day 1/baseline. Subjects receiving rescue therapies during the run-in period are not eligible to participate in the study.

^g Patient-reported outcome assessments and designated safety measurements should occur before investigator assessments, laboratory sample collections, and study drug administration.

^h P/Qs will be implemented in all countries where a validated questionnaire in the local language is available.

ⁱ SD NRS and morning sleep diary questions to be recorded by subjects once daily in the morning and if possible, within 1 hour of getting out of bed (Visit 1/Screening through Visit 6/Week 16). PP NRS, AP NRS, and evening sleep diary questions to be recorded by subjects once daily in the evening (Visit 1/Screening through Visit 6/Week 16), beginning after the screening visit. Topical background therapy use (not including moisturizer) to be recorded by subjects once daily in the evening throughout the study, beginning after the screening visit. On designated visits, PGIS-SD and PGIC-SD should be recorded after the SD NRS and sleep diary in the morning before investigator assessments, laboratory sample collection, and study drug administration; PGIS-P and PGIC-P should be recorded after the PP NRS and AP NRS in the evening the day prior to designated visits.

^j Pruritus assessments (i.e., PP NRS, AP NRS, PCS, PGIS-P, PGIC-P) will be recorded the evening before the clinic visit. If a subject does not complete the PCS, PGIS-P, and PGIC-P in the evening before a scheduled visit, the subject will be allowed to complete the assessment the following day at the clinic visit before investigator assessments, laboratory sample collection, and study drug administration.

^k Assessments to be completed by subjects for 7 consecutive days before the designated target visit dates during study treatment.

^l Optional subject interviews will be conducted at the end of the initial treatment period between Week 16 and Week 18.

^m Optional photographs of AD lesions will be performed only for consenting subjects at selected sites.

ⁿ Subjects with a history of asthma will complete the ACT (and PEF testing) at each scheduled visit. Subjects with de novo asthma will complete the ACT (and PEF testing) beginning from de novo diagnosis and at all subsequent scheduled visits.

^o At screening, the investigator should specifically question all subjects about any medical history of asthma and their respiratory health (eg, wheezing, coughing, allergies, infections). A respiratory examination will be required for all subjects at all scheduled visits.

^p PEF testing will be performed for all subjects at screening, baseline, Week 8, 16, 32, 48, and follow up visits. For subjects reporting a medical history of asthma, PEF testing (and ACT) will be performed at all visits during the clinical study. For subjects diagnosed with de novo asthma, PEF testing (and ACT) will be performed at all visits, starting with the visit in which the diagnosis was confirmed. Subjects should be asked to withhold asthma medication on study visit days until after PEF testing is complete, to the extent it does not pose an undue risk to the subject.

^q Complete PE should be performed at designated visits.

^r Contraceptive counseling should occur at screening or at applicable visits when pre-pubertal subjects begin menses.

^s Height collection will be performed for all subjects at screening. Height collection is only required for adolescents (ages 12-17) at designated post-screening visits.

^t 12-lead ECGs should be performed in the supine position, before any scheduled vital sign measurements and blood draws.

^u Vital signs will include pulse rate, systolic and diastolic blood pressure (after the subject has been sitting for at least 5 minutes), and body temperature.

^v At scheduled visits with laboratory, PK, and ADA assessments, samples are to be collected before study drug injection(s). See hematology, clinical chemistry (including FSH for postmenopausal subjects), and urinalysis testing details, respectively.

^w TB screening: QuantiFERON-TB Gold test for all subjects.

SAP Version: Final Version 1.0, 09-Nov-2022

Controlled Document ID: **3903A.01**, Effective Date 31-Aug-2020

Filing requirements: TMF

CONFIDENTIAL

Statistical Analysis Plan for Interventional Studies

Sponsor: Galderma Research & Development, LLC; Protocol No.: RD.06.SPR.118161

^x Only for WOCBP. Pregnancy test results must be available prior to the administration of the study drug. Serum pregnancy test to be performed at the screening visit; UPT at all other visits. For prepubertal subjects, reconfirm pre-menses status at every visit and, in case of status change, collect information on contraceptive measures and perform a UPT according to the schedule for WOCBP.

^y For postmenopausal subjects (i.e., no menses for 12 consecutive months), confirm status with a high FSH level in the postmenopausal range. Blood chemistry sample at the screening visit (V1) will also be used for an FSH test for the confirmation of postmenopausal status.

^z See details on PK assessments. As a guideline, PK samples should be collected at approximately the same time of day throughout the study, to the extent possible, before study drug injection (pre-dose samples).

^{aa} See details on ADA and PD/biomarker assessments, respectively.

^{bb} Optional PGx sample collection is only for subjects who provide additional consent.

^{cc} All nemolizumab (CD14152)-treated subjects who are clinical responders at Week 16 (defined as 1. IGA of 0 [clear] or 1 [almost clear]; OR 2. EASI-75) will be re-randomized (1:1:1) to receive nemolizumab (CD14152) Q4W, Q8W, or placebo Q4W.

^{dd} Study drug reconstitution will be performed by the pharmacist (or other qualified personnel) throughout the study, and complete reconstitution confirmed, prior to delivery for injection. Study center staff will provide study drug injection training for subjects willing and able to self-inject (or have their caregiver inject) study medication. Subjects and/or caregivers will then be allowed to inject medication at subsequent visits. Based on the subject's preference, study center staff can also perform all injections.

^{ee} After study drug administration, subjects will be monitored closely for any signs or symptoms of hypersensitivity reaction before being discharged. Subjects should remain at the study center for at least 30 minutes after the first 2 injections during the study. *In Germany only, subjects must undergo a 60 minute observation period after the first 3 injections and a 30 minute observation period after all subsequent doses.

^{ff} Subjects will receive a loading dose on Day 1 (i.e., 2 injections of nemolizumab 30 mg or placebo).

^{gg} Subjects will apply a moisturizer daily, and liberally as needed, to dry skin and AD lesions throughout the study. The subject's current moisturizer or a moisturizer recommended by the investigator may be used. Use should not occur within 8 hours before clinic/office visits.

^{hh} Authorized topical therapy use beginning \geq 14 days before Day 1. The investigator should adjust background topical therapy use during the study, according to the disease activity and tolerability, including tapering when signs and symptoms improve, discontinuation when lesions clear, and restarting if signs and symptoms recur, based on investigator clinical judgment.

ⁱⁱ Appropriate amounts of TCS and/or TCI should be dispensed or prescribed at each visit, according to investigator judgement. Containers of previously dispensed/prescribed TCS and/or TCI should be collected at each visit. Collected containers with remaining medication may be re-dispensed back to the subject, when applicable.

^{jj} *No dispensation of TCS and/or TCI should occur at the final study visit. Collection only.*

5. Endpoints

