9.7.4 Pruritus Categorical Scale

The 4-point PCS will be provided for the subjects to report the intensity of their itch during the last 24 hours ([Appendix 15](#)). Subjects will record their PCS score in the evening after completing the Pruritus NRS. If a subject does not complete the PCS in the evening before a scheduled visit, the subject will be allowed to complete the assessment the following day at the clinic visit before investigator assessments, laboratory sample collections, and study drug administration. The PCS will serve as an anchor for the patient-reported outcome (PRO) psychometric validation.

CCI [REDACTED]

[REDACTED]

[REDACTED]

[REDACTED]

CONFIDENTIAL

CCI [Redacted]

[Redacted]

[Redacted]

[Redacted]

[Redacted]

[Redacted]

[Redacted]

[Redacted]

[Redacted]

CONFIDENTIAL

CCI [Redacted]

[Redacted]

[Redacted]

[Redacted]

[Redacted]

[Redacted]

[Redacted]

[Redacted]

[Redacted]

[Redacted]

CONFIDENTIAL

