8.4. Analysis Visit Windows

Efficacy by-visit summaries will use the analysis visit. Unscheduled and early termination visits will be windowed based on the following analysis visit window which is based on study day. If multiple measurements are taken within the same window, the one taken closest to the target study day will be used for the analysis. If there are multiple measurements with same difference from target day, the later assessment should be used for the analysis.

Table 8-1: Analysis Visit Window

Analysis Visit	Target Study Day	Visit Window for EASI, IGA, BSA, SCORAD, Rescue therapy	Visit Window for PGIS-P, PGIS-SD, PGIC-P, PGIC-SD	Visit Window for DLQI/cDLQI, HADS, EQ-5D, POEM, WPAI:AD, Pain intensity/frequency, PGAD, PGAT, PIQs*
Baseline	1	<=1	<=1	<=1
Week 4	29	2 to 42	NA	NA
Week 8	57	43 to 70	2 to 81	2 to 84
Week 12	85	71 to 98	NA	NA
Week 15	106	NA	82 to 108	NA
Week 16	113	99 to 126	>=109	85 to 168 except for PIQs; >=85 for PIQs
Week 20	141	127 to 154	NA	NA
Week 24	169	155 to 182	NA	NA
Week 28	197	183 to 210	NA	NA
Week 32	225	211 to 238	NA	169 to 280 except for PIQs
Week 36	253	239 to 266	NA	NA
Week 40	281	267 to 294	NA	NA
Week 44	309	295 to 322	NA	NA

This document is confidential.

Statistical Analysis Plan for Interventional Studies

Sponsor: Galderma Research & Development, LLC; Protocol No.: RD.06.SPR.118161

Week 48	337	>=323	NA	>=281 except for PIQs
---------	-----	-------	----	-----------------------

* PIQs assessment is available during Initial period only. Visit window after Week 16 will not be applicable for PIQs.

Analysis visit of diary (ePRO) data will be defined depending on the data collection as below.

For the diary data at post-baseline visit, only the diary data assessed within the timeframe below (+1 hour to end time in spec) will be considered for analysis. If >1 diary recorded on a day (within window), only one of them to take for analysis (i.e. latest one for evening diary, earliest one for morning diary).

- Evening assessment (PP/AP NRS, Topical medication, PCS) recorded from 17:00:00 to 00:59:59
- Morning assessment (SD NRS, morning sleep diary) recorded from 5:00:00 to 17:59:59

Consecutive daily assessment:

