In case topical medication used (daily evening assessment throughout the study), 7 days immediately preceding the target study day will be considered to define analysis visit during the study. The same window with evening assessment (PP NRS, AP NRS) in Table 8-2 will be used for Initial Period. For Maintenance Period, the target study day of Week 20, Week 24, Week 28, Week 32, Week 36, Week 40, Week 44 and Week 48 will be Day 141, Day 169, Day 197, Day 225, Day 253, Day 281, Day 309, and Day 337. If the data reported within analysis visit window but after week 16 dosing, it won't be part of initial period. The extended timeframe (+1 hour to end time) to be considered.

Intermittent daily assessment before the visit:

For the evening assessments (PP NRS and AP NRS during Maintenance Period, and PCS assessment), the 7 days immediately preceding the actual subject visit date will be classified into the analysis visit. i.e., from 'actual subject visit date – 7 days' to 'actual subject visit date – 1 day'. Similarly, for the morning assessments (SD NRS, morning sleep diary), the 7 days data from 'actual subject visit date – 6 days' to 'actual subject visit date' will be classified into the analysis visit. In maintenance period, the diary data will not be collected daily, so consider dosing date/time and include data for calculation only if it's done within analysis visit window/timeframe and before dosing.

In case of missing/skipped visit, unscheduled or early termination visit, the diary data will be windowed based on the study day (see Tables 8-3 and 8-4). If a subject missed/skipped a visit due to any reason (e.g., skipped a visit due to COVID-19), the diary data which have been reported during that time will be mapped to the analysis visit based on the study day and 7 days consecutive data will be classified into the analysis visit as in the tables below. For the unscheduled or early termination visit data, the same approach will be applied to window the data into analysis visit.

In case of evening diary (e.g., PP/AP NRS), the data within analysis visit window but after dosing on the clinic visit date will not be used for weekly score calculation at the corresponding analysis visit.

Table 8-3: Analysis Visit Window for Missing/Skipped Visit, Unscheduled or Early termination Visit for PP/AP/SD NRS and Sleep Diary

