Analysis Visit	Target Study Day of Analysis Visit	Visit Window for evening assessment (PP NRS, AP NRS)*	Visit Window for morning assessment (SD NRS, morning sleep diary)
Week 24	169	162 to 168	163 to 169
Week 32	225	218 to 224	219 to 225
Week 40	281	274 to 280	275 to 281
Week 48	337	330 to 336	331 to 337

* for evening diary, only the data before dosing on the clinic visit date will be considered for analysis.

Table 8-4: Analysis Visit Window for Missing/Skipped Visit, Unscheduled or Early Termination Visit for PCS Assessments

Analysis Visit	Target Study Day of Analysis Visit	Visit Window for PCS
Baseline	1	-7 to -1
Week 8	57	50 to 56
Week 15	106	99 to 105
Week 16*	113	106 to 112 before dosing

This document is confidential.

* if <4 days non-missing data within Week 16 window, the upper bound will be extended first up to +5 days to obtain 4 non-missing data. If still <4 non-missing data after extending the upper bound, the lower bound will be extended again up to +5 days to obtain 4 days non-missing data. Only the data before Week 16 dosing (or re-randomization if missing Week 16 dosing) will be considered for Initial Treatment Period analysis.

For efficacy, where two or more assessments (including both scheduled and unscheduled assessments) are available for the same visit interval, the one closest to the target visit date will be used for the summary and analyses. Safety and pharmacokinetics data will not be windowed for by-visit summary. i.e., scheduled visit data will be used for analysis.

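### SAP 8.4 discards nearly all PCS make-up entries that the schedule permits at the clinic visit, and anchors PCS Weeks 15 and 16 differently, so an early Week 16 visit makes them share diary days

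*SAP*

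**What the plan says.** **Collection.** SAP Table 4-3 note j says: "If a subject does not complete the PCS, PGIS-P, and PGIC-P in the evening before a scheduled visit, the subject will be allowed to complete" them at the clinic next day, ahead of the investigator's assessments, blood samples and dosing. Protocol 9.7.4 repeats this for the PCS. Note c sets the Week 15 and Week 16 collection: "For PCS, subjects will complete the assessment for 14 consecutive days before the Week 16 visit". Note k, which the PCS row also carries, instead counts seven days back from target visit dates. Week 15 has no clinic visit.

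**Time-of-day rule (SAP 8.4).** "For the diary data at post-baseline visit, only the diary data assessed within the timeframe below" is considered, and the list that follows includes "Evening assessment (PP/AP NRS, Topical medication, PCS) recorded from 17:00:00 to 00:59:59".

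**Date rule at attended visits (SAP 8.4).** For "PCS assessment), the 7 days immediately preceding the actual subject visit date will be classified into the analysis visit", that is, visit date minus 7 to minus 1.

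**Fixed windows (SAP Table 8-4).** Its title is "Analysis Visit Window for Missing/Skipped Visit, Unscheduled or Early Termination Visit for PCS Assessments". It gives Baseline as Days -7 to -1, Week 8 as 50-56, Week 15 as 99-105 and Week 16 as 106-112 before dosing. A footnote allows Week 16, when fewer than 4 scores exist, to extend its upper bound by up to 5 days and then its lower bound by up to 5 days, using pre-dose data only.

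**Use.** Protocol 9.7.4: "The PCS will serve as an anchor for the patient-reported outcome (PRO) psychometric validation".

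**The concern.** The schedule invites an entry on the visit day, and the analysis rules then have no place for it. Sites and subjects would do what the protocol permits and the score would still be treated as missing.

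The second issue is the pair of PCS weeks before the Week 16 visit. Note c collects both for test-retest validation. If one week is pinned to calendar study days and the other moves with the visit, they can overlap. Two weekly means built partly from the same daily scores agree more than two separate weeks would. If the visit is late, Week 15 may instead have too few collected days to score.

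**Working it through.** **1. Reproduce the plan's windows.** Target day minus 7 to minus 1 (no Day 0) gives Baseline -7 to -1, Week 8 (Day 57) 50-56, Week 15 (Day 106) 99-105 and Week 16 (Day 113) 106-112. All four match Table 8-4.

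**2. Follow a make-up entry made on the visit day before dosing.**

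| Visit | Date rule | Time-of-day rule | Result |
|---|---|---|---|
| Baseline | fails (Day 1) | does not apply | dropped |
| Week 8 | fails | fails if before 17:00 | dropped at any hour |
| Week 16, 4 or more scores | fails | fails if before 17:00 | dropped at any hour |
| Week 16, fewer than 4 scores | can pass through the extension | fails if before 17:00 | kept only if at or after 17:00 and pre-dose |

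No exception is written for the make-up entry, although the SAP waives the time-of-day window elsewhere (the Baseline footnote to Table 8-2). PGIS-P and PGIC-P, covered by the same note j, are not in the time-of-day list and use the wide Table 8-1 windows, so neither rule removes their make-up entries.

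**3. How often a weekly score is lost.** SAP 8.2 requires 4 of 7 daily scores. The make-up entry decides the matter only when the evening before the visit was missed and exactly 3 of the other 6 days were completed. With daily completion p, independent across days, and every missed evening made up:

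loss = C(6,3) × p³ × (1-p)⁴

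- p = 0.85: 20 × 0.6141 × 0.000506 = 0.0062, about 0.6%.
- p = 0.70: 20 × 0.343 × 0.0081 = 0.0556, about 5.6%.

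The documents give no completion rate; both values of p are assumptions. At Week 16 the lower-bound extension must also find nothing, a further factor of (1-p)⁵. At p = 0.70 that is 0.0556 × 0.3⁵ = 0.0556 × 0.00243 = 0.000135, about 0.014%. At p = 0.85 it is effectively zero.

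**4. Weeks 15 and 16 across the ±5-day visit window.** Let v be the actual Week 16 visit day (108 to 118). The Week 16 window is v-7 to v-1; Week 15 is fixed at 99-105. Note c is read as collection on v-14 to v-1, and note k as collection on Days 99-112.

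| v | Week 16 window | Days shared with Week 15 | Week 15 days collected, note c | Week 15 days collected, note k | Week 16 days collected, note k |
|---|---|---|---|---|---|
| 108 | 101-107 | 5 | 7 | 7 | 7 |
| 109 | 102-108 | 4 | 7 | 7 | 7 |
| 110 | 103-109 | 3 | 7 | 7 | 7 |
| 111 | 104-110 | 2 | 7 | 7 | 7 |
| 112 | 105-111 | 1 | 7 | 7 | 7 |
| 113 | 106-112 | 0 | 7 | 7 | 7 |
| 114 | 107-113 | 0 | 6 | 7 | 6 |
| 115 | 108-114 | 0 | 5 | 7 | 5 |
| 116 | 109-115 | 0 | 4 | 7 | 4 |
| 117 | 110-116 | 0 | 3 | 7 | 3 |
| 118 | 111-117 | 0 | 2 | 7 | 2 |

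Under note c, Week 15 falls below 4 days at +4 and +5, and has none left once the visit is 7 or more days late. Under note k, Week 15 is safe and the shortfall moves to Week 16, where the extension may recover it.

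**5. Another route to overlap.** Even with an on-time visit, the Week 16 lower-bound extension can reach from Day 106 back to Day 101, inside Week 15.

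**The case against.** **Always discarded.** A reader might infer that make-up entries are never used. The table in step 2 shows otherwise: the Week 16 extension can admit one recorded late and pre-dose, and at Baseline only the date rule acts. The 0.6% to 5.6% range likewise cannot be carried over to Week 16.

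**Overlap is only a matter of reading.** If Table 8-4 governed both weeks at attended visits, nothing would be shared by the base windows. Its Week 16 row mentions dosing, which suggests that it was not meant only for missed visits. But the SAP text gives attended visits the actual-date rule, and the table title limits the table to other cases. If the title is taken strictly, PCS Week 15 has no window at all. The ambiguity stands and needs settling.

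**Week 15 is lost.** A reader might infer that late visits always empty Week 15. That holds only under note c. Note k, and the zero-day tolerance for Week 15 in the schedule, point to target dates, under which Week 15 keeps all 7 days.

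**Damage to the itch validation.** A reader might infer biased reliability for the PP NRS. The documents do not show that. PP NRS Weeks 15 and 16 have separate fixed windows in Table 8-2 (apart from that table's Week 16 extension), and the psychometric work follows a separate plan (Protocol 10.1.8) that is not available here. The SAP's table index gives PCS only an observed-case descriptive summary, and daily PCS values are listed. Parts of SAP 10.3 are blacked out, so any PCS scoring text there cannot be checked.

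**Recall period.** A clinic entry covers the 24 hours before it, not exactly those before the missed evening. That is fair, but note j already accepts this by permitting the entry.

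**Conclusion.** The conflict between note j (with Protocol 9.7.4) and SAP 8.4 is real and comes from stated rules. A permitted PCS make-up entry is excluded at Baseline and Week 8 by date, and by time of day as well when it is post-baseline and before 17:00. It is excluded at Week 16 except in the narrow case described. The cost is at most about 0.6% to 5.6% of weekly scores at Baseline or Week 8, under assumed completion of 85% to 70%, independent days and universal make-up. At Week 16 it is almost nil, provided the Table 8-4 footnote applies to attended visits.

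The different anchors produce 1 to 5 shared days of 7 when the Week 16 visit is 1 to 5 days early, taking Days 99-105 as the Week 15 window because no other is given. Whether Week 15 can also fall short at +4 or +5 days is open until notes c and k are reconciled.

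This is a minor point. PCS is descriptive in this SAP, and no primary or key secondary result changes.

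**What to change.** In SAP 8.4:

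- (a) Count a PCS entry completed at the clinic before dosing on the visit date as the previous evening's entry, exempt from the time-of-day filter.
- (b) State one anchor for PCS Weeks 15 and 16 at attended, in-window visits, for example visit minus 14 to minus 8 and visit minus 7 to minus 1. With note c collection this gives no shared days and 7 of 7 possible Week 15 days for every v. Keep fixed study-day windows for a missed Week 16 visit or one delayed by COVID-19; Protocol Appendix 2 allows a delay of up to 8 weeks, which would carry a visit-anchored Week 15 far off target.
- (c) Stop the Week 16 lower-bound extension from reusing Week 15 days.
- (d) Reconcile notes c and k on whether collection runs to the actual or the target date.

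The cost is a few sentences and a small programming change, with no new data. One downside is that a visit-anchored PCS Week 15 may differ by a few days from the fixed PP NRS Week 15 window.
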